9.4	RECORDS RETENTION	41
10	STUDY MONITORING, AUDITING, AND INSPECTING	41
10.1	STUDY MONITORING PLAN	41
10.2	AUDITING AND INSPECTING	42
11	ETHICAL CONSIDERATIONS.....	42
12	STUDY FINANCES.....	42
12.1	FUNDING SOURCE.....	42
12.2	CONFLICT OF INTEREST	42
13	PUBLICATION PLAN.....	43
14	REFERENCES.....	43
15	ATTACHMENTS	50
15.1	INVESTIGATIONAL DRUG BROCHURE FOR AIR001	ERROR! BOOKMARK NOT DEFINED.
15.2	CHARTER FOR DATA SAFETY AND MONITORING BOARD	ERROR! BOOKMARK NOT DEFINED.
15.3	SCHEDULE OF ASSESSMENTS	50

LIST OF ABBREVIATIONS

AE	Adverse Event/Adverse Experience
CFR	Code of Federal Regulations
CRF	Case Report Form
DSMB	Data and Safety Monitoring Board
FDA	Food and Drug Administration
GCP	Good Clinical Practice
HIPAA	Health Insurance Portability and Accountability Act
IB	Investigator's Brochure
ITT	Intent to Treat
IND	Investigational New Drug Application
IRB	Institutional Review Board
IP	Investigational Product
PHI	Protected Health Information
PI	Principal Investigator
SAE	Serious Adverse Event/Serious Adverse Experience
SOP	Standard Operating Procedure

Study Summary

Title	Inorganic Nitrite To Amplify the Benefits and Tolerability of Exercise Training In Heart Failure With Preserved Ejection Fraction
Protocol Number	16-001467
Phase	Phase II
Methodology	
This is a randomized, blinded, placebo-controlled, two-stage, parallel-group clinical trial with all subjects receiving exercise training (ET) and randomized to either inorganic sodium nitrite or matching placebo.
 
The trial includes 2 stages. In stage I, which has been completed, patients received inhaled nitrite/placebo. In stage II, patients will receive oral nitrite/placebo.

Overall Study Duration	4 years
Subject Participation Duration	14 weeks
Single or Multi-Site	Single site
Objectives	To determine if sodium nitrite can improve the clinical responses to ET in subjects with heart failure and preserved ejection fraction (HFpEF).
Number of Subjects	100 (36 received inhaled nitrite/placebo in the completed stage I, up to another 64 will receive oral nitrite/placebo in stage II of the study)
Diagnosis and Main Inclusion Criteria	
Heart failure with preserved ejection fraction (HFpEF) defined by clinical heart failure, normal EF ($\geq 50\%$) and at least one of the following:
 
 • Previous hospitalization for HF with radiographic evidence (pulmonary venous hypertension, vascular congestion, interstitial edema, pleural effusion) of pulmonary congestion or • Catheterization documented elevated filling pressures at rest or with exercise or • Elevated NT-proBNP (>400 pg/ml) or • Echo evidence of diastolic dysfunction/elevated filling pressures manifest by medial E/e' ratio ≥ 15 and/or left atrial enlargement and chronic treatment with a loop diuretic for signs or symptoms of heart failure
Study Product, Dose, Route, Regimen	
Stage I tested Inhaled, nebulized sodium nitrite (AIR001) 80 mg at least 4 hours apart three times daily during waking hours (i.e. 08:00, 12:00, 16:00).
 
Stage II is testing oral nitrite 40 mg tid capsules vs matching placebo capsules (same dosing frequency).

Duration of Administration	12 weeks
Reference therapy	Placebo
Statistical Methodology	Data will be analyzed according to ITT principles (assigned group regardless of study drug administration or compliance with ET benchmarks achieved). Primary hypotheses will be tested using a two-sample t-test on the change (baseline to 12 week). Testing will be stratified by route of administration.

1 Introduction

Heart failure with preserved ejection fraction (HFpEF) afflicts millions of older Americans and is associated with exercise intolerance, reduced quality of life (QOL), high health care costs, and increased mortality. People with HFpEF display increased cardiac filling pressures and inadequate cardiac output reserve to deliver blood to the body during exercise. Numerous lines of evidence have implicated abnormalities in nitric oxide-cyclic guanosine monophosphate (NO- cGMP) signaling as playing a key role in promoting these abnormalities. While there is currently no proven effective medical treatment for HFpEF, exercise training (ET) has been shown to improve aerobic capacity and QOL in this population.

However, ET provides benefits through peripheral effects in the muscles and vasculature, without targeting the cardiac limitations. The specific objectives of this application are to determine whether treatment with sodium nitrite (which improves the cardiac abnormalities) in addition to ET can improve exercise capacity, chronic activity levels, and QOL in people with HFpEF as compared to ET alone. The guiding hypothesis is that enhancing NO-cGMP signaling in the heart and periphery preferentially during exercise will improve functional capacity and symptoms in HFpEF above and beyond what is seen with ET alone. Conversion of nitrite (NO_2^-) to biologically active NO is enhanced during tissue hypoxia and acidosis, which develop during low-level exercise in HFpEF, so it is expected that this intervention will preferentially target the cardiac limitations that develop during exercise in these patients at the time of greatest need.

This document is a protocol for a human research study. This study will be carried out in accordance with the applicable United States government regulations and Mayo Clinic research policies and procedures.

1.0 Summary of Protocol Changes and Rationale

Significant delays in obtaining study drug supply have forced us to make another modification to this study. In the last modification to the protocol two main changes were made: (1) we changed the route of administration of sodium nitrite from inhaled to oral, and (2) we have decreased the duration of intervention for endpoint assessment from 12 to 10 weeks. In this modification, we are changing the duration of treatment back to 12 weeks to align with what was done in the first Stage of the study, and we are changing the randomization ratio to 2:1 for nitrite relative to placebo, for the reasons enumerated below.

In the first Stage of the study, nitrite/placebo was administered in an inhaled formulation. However during the enrollment period, development of this product was discontinued by the manufacturer. In order to test the primary study hypotheses, we have switched from an inhaled formulation of nitrite to an oral formulation that achieves similar pharmacokinetics for Stage 2 of the study.

Since that time, the research pharmacy that was compounding our study drug (Triangle Pharmacy) has ceased production, forcing us to identify and work with a new pharmacy (RXQ) which has

introduced a very large delay because of the longer start up process, and the need for additional batch testing. After one shipment was received, RXQ Pharmacy failed to deliver further shipments of study drug and has not met production requirements, forcing us to again change the compounding pharmacy to The University of Iowa Pharmaceuticals (Iowa City, Iowa; uip.pharmacy.uiowa.edu). Potency and stability testing will be performed at University of Pittsburgh laboratories prior to release of study drug batches

We had planned to enroll another 68 patients, 34 receiving oral nitrite and 34 receiving oral placebo. However, we cannot meet this goal in two years. Our revised plan to meet our recruitment goal will be to use the data from the 17 patients receiving inhaled placebo in the first phase of the study. We will then combine these data with that from patients receiving oral placebo drug moving forward. Because we do not expect the response to inhaled and oral placebo to differ, we feel that this is scientifically justified.

Therefore, we will only require complete data from another 17 patients receiving oral placebo (for a combined total of 34 placebo patients) and another 34 patients receiving oral nitrite, for a total of 51 patients in the oral phase with complete data. Because more data is needed for patients randomized to nitrite, we will randomize patients in a 2:1 ratio moving forward of nitrite to placebo.

We have enrolled 14 patients according to the last protocol modification (on oral drug, which has been very well-tolerated). Therefore, at this time we will require complete data on another 47 patients. To allow for participant drop out and incomplete data, we will enroll up to another 60 patients to meet our goal of reaching another 47 with complete data.

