6.2 Exercise Training (ET) Visits

Following the screening visit 1, subjects will enroll in standard cardiopulmonary exercise training (cardiac rehab) in the Mayo Cardiovascular Health Clinic (CVHC). This will involve ~1 hour sessions 3 times weekly wherein subjects participate in a combination of endurance and strength training as per current practice in the Mayo CVHC. As a result of COVID-19, Mayo Clinic

(Rochester and Health System sites) cardiac rehabilitation centers remain closed or are open with significantly reduced capacity. Thus, we feel it prudent to offer our participants (who are all considered high-risk for contracting COVID-19) a home-based cardiac rehabilitation program (HBCR). This program will model the center-based cardiac rehab program implemented by the Mayo Clinic CVHC. Participants who agree to complete the HBCR program will be seen in clinic for their baseline assessments, 6 minute walk, and given a home exercise protocol. A member from the study team will follow up with patient twice weekly to assess program compliance, discuss successes/barriers with the exercise program, provide modifications to the exercise program (if necessary) and offer support and encouragement.

Once weekly, adverse events, safety and tolerability will be assessed., along with promotion of adherence to training regimen (for example on the third ET visit of each week). For Mayo health system participants this assessment will be done during a weekly telephone call. Every other week, study drug compliance information will be downloaded from the I-Neb device (for Stage I), reviewed, and discussed with the participant. For Mayo health system participants the I Neb device will be downloaded and reviewed during the week 4 visit, week 8 visit and final visit (for Stage I). For Stage II, adherence will be assessed by pill counts at these visits and review of diary.

ET Visit 1:

At the first ET visit (ET1), subjects received training on the use of I-neb device to administer study drug (for Stage I only). For Stage II, subjects will take their first dose of oral study drug 30 minutes prior to the initiation of the ET session (at ET1 and all training visits). One to two days after ET Visit 1, a study team member will call the participant at home to ask about compliance and tolerability of study drug.

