7.1 Statistical Overview

7.2 The full statistical details for this protocol are documented in the supplementary Statistical Analysis Plan (SAP). This protocol provides the key information, namely the justification for the sample size and the details on the primary analysis. The details regarding secondary endpoints, subgroup analyses, missing data and analysis sets are provided in the SAP. **Sample Size Determination**

In the RELAX trial, the mean \pm SD change in peak VO₂ with placebo in subjects with HFpEF treated for 6 months was 0 ± 2.0 ml/kg/min,³⁶ and in a previous trial of ET in HFpEF, the increase in peak VO in the ET arm was $+2.3\pm 2.2$ ml/kg/min.²² An increase of 75% (additional 1.5 ml/kg/min) in this change would be considered clinically relevant. Thus, we estimate that a sample size of N=34 participants per group will be required to provide 80% statistical power (two-tailed, alpha=0.05) to detect the difference of 1.5 ml/kg/min between subjects randomized to NO₂⁻ with ET versus placebo with ET. To account for attrition, we will increase our number of randomized subjects to 40/group (enroll 80 subjects total to accrue 68 total or 34 in each group).

Stage 1 was discontinued early because of loss of inhaled nitrite availability, therefore we will accrue a total of 68 patients with complete data combining the patients with complete data receiving inhaled placebo in Stage I (n=17) with another 51 patients in Stage II (17 receiving placebo and 34 receiving nitrite) to ensure that the study is adequately powered to test the study hypotheses.

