7.3 Primary Outcome Analysis

Primary Statistical Hypotheses:

H0: Change from baseline to 12 weeks in Peak VO₂ in participants randomized to NO₂⁻ will be equal to the change in Peak VO₂ in participants randomized to placebo.

Ha: The change from baseline to 12 weeks in Peak VO₂ will be different between the two randomized groups

Analysis Summary:

The primary statistical hypothesis will be tested using a regression framework. The dependent variable will be the change (baseline to 12 week) in Peak VO₂. An indicator variable will be used to indicate the randomized treatment assignment (NO₂⁻ vs. placebo as the referent). This analysis is equivalent to a two-sample t-test. While the study design is randomized, the number of participants is relatively small, so imbalance between putative confounding variables may be observed. To address this, we will conduct an a priori sensitivity analysis that will adjust for baseline Peak VO₂, BMI, Sex, and Age group strata through an extension of the regression model used for the primary analysis. The type III estimate of the treatment effect will be compared to the unadjusted estimate to assess the robustness of the randomization process.

Statistical testing for the primary analysis will be two-sided at the alpha=0.05 level of significance.

8 Safety and Adverse Events

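### Stage II moved from an apparent 1:1 plan to 2:1 allocation, but nothing in the primary analysis separates the two oral periods, so part of any between-period difference in response enters the treatment estimate

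*Combined protocol and SAP*

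**What the plan says.** Section 1.0 gives the earlier Stage II plan as "34 receiving oral nitrite and 34 receiving oral placebo", which implies 1:1, although no ratio is written there or in Section 5.3. It then announces the change: "we will randomize patients in a 2:1 ratio moving forward of nitrite to placebo". By that point, "We have enrolled 14 patients according to the last protocol modification". The same section says that the previous modification had shortened the intervention to 10 weeks and that this one returns it to 12.

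The Stage II target is 51 patients with complete data (34 nitrite, 17 placebo). They are to be combined with 17 Stage I inhaled-placebo patients to give 34 v 34.

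Section 7.3 regresses the change in peak VO2 on treatment alone: "An indicator variable will be used to indicate the randomized treatment assignment". It describes this as equivalent to a two-sample t-test. The sensitivity model adds baseline peak VO2, BMI, sex and age group. Neither model has a term for period, stage or allocation ratio. The Study Summary says that testing is stratified by route; Section 7.3 does not repeat this.

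**The concern.** Once the allocation ratio changes, the period in which a patient was randomised predicts the arm. Within each period the comparison is still randomised, but a single difference of means taken across both periods is not fully protected. If mean response differs between periods, the arm with more late patients (nitrite) absorbs more of that difference.

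The documents give a reason to expect a difference. The ratio and the intervention length changed in the same modification, so the early oral patients appear to have enrolled under a 10-week plan. The Study Assessments text still places the Stage II exercise test at week 10, which must be reconciled with the 12-week endpoint. Home-based rehabilitation was offered later, from July 2020.

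The direction is not fixed. A higher response in the later period would favour nitrite; a lower one would count against it. The sensitivity covariates are patient characteristics and would not capture a change in how training or assessment was done.

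**Working it through.** **Inputs.** Difference 1.5 ml/kg/min: "An increase of 75% (additional 1.5 ml/kg/min) in this change would be considered clinically relevant" (Section 7.2, Sample Size Determination). Test: "Statistical testing for the primary analysis will be two-sided at the alpha=0.05 level of significance" (Section 7.3). SD 2.2, from the earlier exercise-training trial cited in Section 7.2. That section also quotes 2.0 and does not say which was used. Counts are from Sections 1.0 and 7.2. The 7/7 split of the first 14 (or 2/2 of 4) and the step sizes are assumptions; the documents give neither.

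**The plan's own figure.** "sample size of N=34 participants per group will be required to provide 80% statistical power". n = 2(1.96 + 0.842)² × 2.2² / 1.5² = 33.8, so 34 per group, with power 80.3% by the normal approximation (79.1% by noncentral t). SD 2.0 would give 28, so 2.2 is the SD that reproduces 34.

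**Counts.** Section 1.0 asks for 47 more complete patients after the first 14, but 51 − 14 = 37. Conversely, 51 − 47 = 4. The enrolment ceilings show the same gap: the Study Summary allows up to 64 oral patients, Section 1.0 up to 60 more, and 64 − 60 = 4. Whether 14, 4 or some other number of early patients enter the analysis is unclear, so both are carried below.

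**Leakage factor in the Stage II contrast.** Bias = k × step, where k = (share of nitrite patients in the 2:1 period) − (share of placebo patients in the 2:1 period). For the 34/17 target with all 14 counted: 27/34 − 10/17 = 0.794 − 0.588 = 0.206.

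Unadjusted SE = 2.2 × √(1/n₁ + 1/n₀). SE with a period term = 2.2 / √Σ[n₁n₀/(n₁ + n₀)], summed over periods. Type I error = 1 − Φ(1.96 − bias/SE) + Φ(−1.96 − bias/SE).

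| Early, then late (nitrite/placebo) | k | Bias, step 0.5 to 1.0 | Type I error, step 1.0 | SE without, with period term |
|---|---|---|---|---|
| 7/7, then 27/10 (34/17 target) | 0.206 | 0.10 to 0.21 | 6.1% | 0.653, 0.670 |
| 7/7, then 37 at exactly 2:1 | 0.141 | 0.07 to 0.14 | 5.6% | 0.635, 0.643 |
| 7/7, then 47 at exactly 2:1 | 0.126 | 0.06 to 0.13 | 5.5% | 0.583, 0.589 |
| 2/2, then 32/15 (34/17 target) | 0.059 | 0.03 to 0.06 | 5.1% | 0.653, 0.657 |
| 2/2, then 47 at exactly 2:1 | 0.053 | 0.03 to 0.05 | 5.1% | 0.647, 0.650 |

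**Cost within Stage II, first row.** Information with the term is 49/14 + 270/37 = 3.50 + 7.30 = 10.80, so SE = 2.2/√10.80 = 0.670 against 0.653, a rise of 2.5%. Power for 1.5 goes from 63% to 61%.

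**Cost in the pooled 34 v 34 model.** Unadjusted SE = 2.2 × √(2/34) = 0.534, power 80%.
- Stage I placebo grouped with the 1:1 period (7/24, then 27/10): information 168/31 + 270/37 = 5.42 + 7.30 = 12.72, SE 0.617, power 68%.
- Stage I as its own stratum: its 17 placebo patients have no inhaled-nitrite counterpart in this set and add nothing, so SE is 0.670 and power 61%.
- Stratifying by route alone already gives SE 0.653 and power 63%.

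**The case against.** The case against acting is reasonable. The effect is small: the largest bias in the table, 0.21, is about a third of one standard error (0.21/0.653 = 0.32). The step is assumed, the earlier 1:1 ratio is inferred, and the top factor of 0.206 needs a 27/10 split of the later patients, which is 2.7:1 rather than 2:1. If only 4 early patients count, the factor is about 0.05 to 0.06. The primary comparison in Section 7.2 is also the pooled 34 v 34 set, where a period term costs far more than 2.5%. Section 7.1 refers to a fuller statistical plan that is not in the text supplied, though it also says that the protocol gives the primary-analysis details.

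Most of this stands and sets the size of the point. It does not remove it: under every reading of the counts the factor is above zero, and neither Section 7.3 nor route stratification addresses it.

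A reader might infer that any change over time in training response is confounded with treatment. The documents do not support that. The ratio is constant within each period, so drift inside the 2:1 period is not confounded by this mechanism. The same applies to home-based rehabilitation: it matters only as far as it shifts the mean of the later period, and nothing shows that it began when the ratio changed.

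**Conclusion.** The point holds as a modest, partial confounding. Between about 5% and 21% of a step in mean response at the ratio change would enter the Stage II treatment contrast. That is a bias of about 0.03 to 0.21 ml/kg/min for an assumed step of 0.5 to 1.0, or 2% to 14% of the 1.5 target (0.03/1.5 and 0.21/1.5). Type I error at a 1.0 step is about 5.1% to 6.1%. These figures rest on SD 2.2, an even split of the early patients and the assumed steps. The lower end applies if only 4 early patients are analysed.

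A larger effect might be read into the pooled comparison, where half of a step passes through (27/34 − 10/34 = 0.50) and a 1.0 step gives type I error of 15.5%. That should not be charged to the ratio change. A step between Stage I and Stage II, which does not depend on the Stage II ratio change, gives the same 0.50 (34/34 − 17/34). Borrowing non-concurrent Stage I placebo is a separate and larger issue.

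**What to change.** In Section 7.3:
1. Carry over the stratification by route already stated in the Study Summary, so that the two sections agree.
2. Within the oral stratum, add a fixed term for allocation period (1:1 v 2:1), so that patients are compared within the ratio under which they were randomised.
3. State explicitly how Stage I placebo patients are coded.

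In Section 1.0, state the earlier Stage II ratio, reconcile 14, 47 and 51, and say which early oral patients enter the analysis and at which week their endpoint was measured.

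Allocation period is known for every patient, so no new data are needed. Beyond route stratification, the cost is at most about 2.5% in the Stage II standard error (power 63% to 61%), and less under the other count scenarios. If the term is put in the pooled 34 v 34 model instead, the standard error rises from 0.534 to 0.617 or 0.670 and power falls from 80% to 68% or 61%, depending on the Stage I coding. Most of that loss comes from no longer borrowing Stage I placebo: route stratification alone already gives 63%. The plan should say so, so that the loss is not attributed to the period term.

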3.2 Primary Study Endpoints

Exercise capacity assessed by peak oxygen consumption (VO₂) achieved during exercise testing will be the primary endpoint for Aim 1. Chronic activity levels assessed by accelerometry will be the primary endpoint for Aim 2. Assessments were performed after 12 weeks of intervention.

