Measurement of QOL will be performed every other week at ET sessions using the Kansas City Cardiomyopathy Questionnaire (KCCQ).^{56, 57} The KCCQ score reflects clinical status in HF with high fidelity;^{56, 57} the score changes rapidly with clinical improvement or deterioration,^{58, 59} is strongly associated with outcome,⁶⁰ and performs equally well in HFpEF and HFrEF.⁶¹ The SF36 will be completed at the screening visit and final endpoint visit (week 12).

Endothelial function will be assessed at Visit 1 and Visit 2 using digital arterial tonometry (reactive hyperemia peripheral arterial tonometry, RH-PAT, EndoPAT, Itamar Medical).⁹ These noninvasive assessments are routinely performed for both research and clinical care purposes. Changes in activity level, QOL and symptoms will then be correlated with changes in microvascular endothelial function (RH-PAT).

Assessment of Exercise capacity will be performed at Visit 1 (pre drug) and Visit 2 (week 10 for Stage II of study) using expired gas analysis in the laboratory of [name] (Joseph 4).

Subjects participating in the additional ancillary study will also undergo an additional cardiopulmonary exercise test at the final ancillary study visit. Participants will undergo standard, maximal effort cardiopulmonary testing on a semi-recumbent cycle ergometer to maximal subjective effort level with assessments of gas exchange as described below:

- Measurement of Gas Exchange and Ventilation will be performed during exercise testing to measure the volumes of VO₂, carbon dioxide produced (VCO₂), breathing frequency (fb), tidal volume (VT), minute ventilation (VE), partial pressure of end-tidal oxygen and carbon dioxide (PETO₂ and PETCO₂), and derived variables (e.g., respiratory exchange ratio, VE/VCO₂, etc.) using a low resistance, open circuit, automated metabolic system (Medical Graphics Co., St. Paul, MN) integrated to a mass spectrometer (Perkin Elmer, model 1100) as we have previously described.^{4,9,13,35,36}
- Cardiac Output (CO) will be measured at rest and during exercise by the acetylene (C₂H₂) wash-in technique first described by Stout et al., refined by Gan et al. and Nielson et al. and validated against direct Fick in our laboratory.⁴⁵⁻⁴⁸

Echocardiography will be performed at rest and during exercise at Visit 1 and Final Visit to estimate central cardiac hemodynamics and ventricular function, including EF, Doppler-estimated pulmonary artery systolic pressure, and LV filling pressures (E/e' ratio).

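### Stage II's primary exercise test is placed at both week 10 and week 12, with no rule in the supplied text for week-10 values and counts of early oral patients that do not reconcile

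*Combined protocol and SAP*

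**What the plan says.** **Week 12.** Section 7.3 reads "The dependent variable will be the change (baseline to 12 week) in Peak VO"2, with no exception by stage. Section 3.2 agrees: "Assessments were performed after 12 weeks of intervention". Section 3.1 gives oral study drug for the full 12 weeks in Stage II. The schedule in section 15.1, as far as the extracted table can be read, has the cardiopulmonary exercise test at a final visit in week 12.

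**Week 10.** The exercise-capacity paragraph among the study assessments of section 6.5.3 puts Visit 2, the post-treatment test, at "week 10 for Stage II of study". This is procedure text, not amendment history.

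**History.** Section 1.0 says of the previous modification that "we have decreased the duration of intervention for endpoint assessment from 12 to 10 weeks", and of the present one that "we are changing the duration of treatment back to 12 weeks to align with what was done in the first Stage of the study". It then states: "We have enrolled 14 patients according to the last protocol modification".

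**Counts.** Section 7.2 needs 68 complete patients: 17 Stage I inhaled-placebo patients and "another 51 patients in Stage II (17 receiving placebo and 34 receiving nitrite"). Section 1.0, after mentioning the 14, asks for complete data on another 47 and allows up to another 60 to be enrolled. The Study Summary allows up to 64 in Stage II, within a total of 100.

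**The concern.** The primary outcome is a change over a fixed period, and the plan gives two periods for the same test. That leaves two questions open.

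The first is what happens if the week-10 text is followed. Half of the planned control group (17 of 34) comes from Stage I, which ran for 12 weeks, while all 34 nitrite patients come from Stage II. A week-10 test in Stage II would therefore give every nitrite patient, but only half of the controls, the shorter period of training. The arms would differ in duration as well as in drug.

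The second is what happens to patients enrolled while the 10-week endpoint was in force. Read literally, section 7.3 makes a week-10 test something other than the primary outcome. Leaving it out loses a randomised patient from an analysis that the Study Summary describes as intention-to-treat. Using it mixes two durations under a 12-week label. Without a rule written in advance, the choice could be made with results in view. How many patients this concerns cannot be read from the plan, because its counts do not fit together.

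**Working it through.** **Inputs.** Section 7.2: difference 1.5 ml/kg/min, 34 per group, two-sided alpha 0.05, 80% power, training gain 2.3 with SD 2.2 from an earlier exercise-training trial, and SD 2.0 from the placebo arm of the cited sildenafil trial. Section 7.2 does not say which SD was used.

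**The plan's own figure.** n = 2(1.960 + 0.842)² × 2.2² / 1.5² = 33.8, so 34 per group. SD 2.2 reproduces the plan; SD 2.0 gives 28. The normal approximation gives 80.3% power for 34 v 34. The noncentral t, used below, gives 79.1%.

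**Assumptions for what follows.** Training gain and nitrite effect grow in proportion to weeks, so a week-10 value is 10/12 of a week-12 value. The 14 early patients were split 7:7, as inferred from the former 34:34 plan. The documents state neither.

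**Case A: all of Stage II tested at week 10, Stage I placebo at week 12.**
- Nitrite: (2.3 + 1.5) × 10/12 = 3.167.
- Placebo: (17 × 2.3 + 17 × 2.3 × 10/12) / 34 = 2.108.
- Difference: 3.167 − 2.108 = 1.058.
- Power at 34 v 34: 49.8%.

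The loss has two parts. Shorter drug exposure takes 1.5 to 1.5 × 10/12 = 1.25. Unequal duration between the arms takes off a further 2.108 − 2.3 × 10/12 = 0.19, and would do so even if nitrite had no effect.

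The result depends on the proportional assumption. With half that loss (factor 11/12) the difference is 3.8 × 11/12 − (17 × 2.3 + 17 × 2.3 × 11/12) / 34 = 1.28 and power is 65.6%. With no gain between weeks 10 and 12 there is no loss.

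**Case B: only early patients have week-10 values, and these are used.**
- Four count (2:2) within 34 v 34: 1.5 × (32 + 2 × 10/12) / 34 = 1.485.
- Fourteen count (7:7) within 34 v 34: 1.5 × (27 + 7 × 10/12) / 34 = 1.449.
- Fourteen are added to 47 new completers. At 2:1 the 47 give about 31 nitrite and 16 placebo, so the groups are 31 + 7 = 38 and 16 + 7 + 17 = 40. Nitrite: 3.8 × (31 + 7 × 10/12) / 38 = 3.683. Placebo: 2.3 × (33 + 7 × 10/12) / 40 = 2.233. Difference: 1.450.

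| Case | Groups | Difference | Power, SD 2.2 | Power, SD 2.0 |
|---|---|---|---|---|
| As planned | 34 v 34 | 1.50 | 79.1% | 86.1% |
| A: all Stage II at week 10 | 34 v 34 | 1.06 | 49.8% | 57.5% |
| B: 4 early patients | 34 v 34 | 1.49 | 78.3% | 85.5% |
| B: 14 early patients | 34 v 34 | 1.45 | 76.3% | 83.7% |
| B: 14 added to 47 new | 38 v 40 | 1.45 | 81.9% | 88.5% |
| Early patients left out, 47 new only | 31 v 33 | 1.50 | 76.5% | 83.9% |

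**Counts.** 17 + 34 = 51 and 17 + 51 = 68 are correct. But 51 − 14 = 37, not 47, and 14 + 47 = 61, not 51. Likewise 14 + 60 = 74, not 64. With 4 in place of 14, both sums close: 4 + 47 = 51 and 4 + 60 = 64. So either only 4 of the early patients are meant to count, or one of the figures is wrong. The text does not say which.

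**The case against.** A reader might infer that all 14 early patients lack a week-12 test, so that their primary outcome does not exist and the 51 cannot be reached. The documents do not support this. Section 1.0 says that they were enrolled, not that they finished or were tested at week 10; some may have continued to week 12. The 51 is a complete-data target whose sum is correct, and the request for another 47 leaves only 4 places for early patients. Section 7.2 implies 15% attrition (80 enrolled for 68 complete). At that rate 60 further patients would give 60 × 0.85 = 51 completers without any of the 14.

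A second defence is that the week-10 phrase in section 6.5.3 is left over from the previous modification, since the same section puts the IPAQ and SF-36 at a final visit in week 12. That is plausible, and it makes Case A a consequence of following the text rather than a forecast. It does not remove the contradiction: the phrase is attached to the primary test itself. The past tense in section 3.2 might also be read as describing Stage I alone, but section 7.3 is not limited in that way.

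A third is that section 7.2 leaves missing data and analysis sets to a supplementary SAP, which is not in the supplied text. A rule for week-10 values may be there. This stands as a limit on the point, so it cannot be said that no rule exists anywhere. Section 7.3 nevertheless defines the outcome and should agree with the procedures.

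**Conclusion.** The point holds as a contradiction over the timing of the primary test, with an unstated rule for any week-10 values and counts that do not reconcile. It does not show that 12-week outcomes are missing for any patient.

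The size depends on which text was followed. If week 10 applied to the whole of Stage II, pooling with 12-week Stage I controls would bias the comparison against nitrite, and power could fall to about 50% at SD 2.2 (about 58% at SD 2.0). That is the lower end of a range that rests on gains proportional to weeks; with a plateau by week 10 nothing is lost. If only early patients are affected, power moves by about three percentage points at most in either direction in the cases worked above. There the defect is an undefined primary outcome rather than a material loss of power.

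**What to change.** 1. Reconcile the exercise-capacity text in section 6.5.3 with sections 3.1, 3.2, 7.3 and 15.1, so that the Stage II test has one stated time.
2. Before unblinding, state in section 7.3 how any week-10 tests already obtained enter the primary analysis (for example, as the end-of-intervention value) and give their number by arm.
3. Prespecify a sensitivity analysis limited to week-12 tests.
4. Reconcile 14, 47 and 51 in sections 1.0 and 7.2, and 60 in section 1.0 with 64 in the Study Summary. State how many early patients count toward the 51.
5. If the resulting numbers fall below 34 per group, restate the power and name the SD used.

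If the supplementary SAP already holds a rule for week-10 values, a cross-reference in section 7.3 would meet step 2. The cost is wording and one extra analysis, with possibly a slightly lower stated power.
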